#### **10.2.6 Clinical Laboratory Assessments**

Any abnormal clinical laboratory test results determined to be clinically significant by the investigator should be repeated (at the investigator's discretion) until the cause of the abnormality is determined, the value returns to baseline or to within normal limits, or the investigator determines that the abnormal value is no longer clinically significant.

All clinical laboratory result pages should be initialed and dated by an investigator, along with a comment regarding whether or not the result is clinically significant.

The diagnosis, if known, associated with abnormalities in clinical laboratory tests that are considered clinically significant by the investigator will be recorded in the AE eCRF.

AEs will be graded using NCI-CTCAE v 5.0 criteria.

##### **10.2.6.1 Hematology**

Hematology assessments include CBC with differential, platelets, and hemoglobin.

##### **10.2.6.2 Serum Chemistry**

Serum chemistry assessments will include blood urea nitrogen, creatinine, alanine aminotransferase, aspartate aminotransferase, alkaline phosphatase, lactate dehydrogenase, total bilirubin, direct bilirubin, total protein, sodium, potassium, chloride, bicarbonate, calcium, phosphate, magnesium, and glucose.

##### **10.2.6.3 Fasting Lipid Profile**

The fasting lipid profile will include total cholesterol, high-density lipoprotein cholesterol, low-density lipoprotein cholesterol, and triglycerides.

##### **10.2.6.4 Coagulation**

The coagulation assessment will include INR and PTT.

#### 10.2.6.5 Urinalysis

Urine samples will be collected and macroscopic assessment of the amount of protein, glucose, white blood cells, and red blood cells will be performed (levels should be recorded if available) and microscopic analysis will be performed if an abnormality is noted.

#### 10.2.6.6 Pregnancy Testing

Serum pregnancy tests will be performed only in women of child-bearing potential. Either serum or urine pregnancy test will be performed within 3 days prior to C1D1 and every cycle thereafter and at the EOT visit.

#### 10.2.7 Adverse Events

Adverse events will be recorded after administration of the first dose of study drug (AEs reported between signing the informed consent form and before C1D1 dose administration will be captured as medical history).

#### 10.2.8 Prior and Concomitant Medications

All prescription and over-the-counter medications taken by a subject within 30 days before the first study drug administration will be recorded in the designated electronic CRF (eCRF). Any concomitant medications added or discontinued during the study should be recorded in the eCRF.

### 10.3 Procedures to Assess Efficacy (Biopsy and Disease Assessment)

#### 10.3.1 Radiologic Assessments

Computed tomography (with contrast) or MRI of chest, abdomen, and pelvis must be obtained within 28 days prior to the first IP dose. The same method (CT with contrast or MRI) must be used throughout the study. Subjects with brain metastasis should have MRI scans of the brain.

Radiographic assessment (and physical assessments of malignancy) should be performed at every 2 cycles starting at C3 (ie, C5, C7, C9, etc). Assessments must be performed prior to commencing treatment for that cycle. Post C9 assessment, subjects who have been determined to have obtained a clinical benefit from OP-1250 may reduce frequency of assessments to every 3 cycles (ie, C12, C15, C18, etc.) prior to commencing treatment for that cycle.

#### 10.3.2 Tumor Assessments

Tumor assessments will be performed on subjects who have not previously progressed in the study, unless completed within the previous 4 weeks. Overall response (CR and PR) as

[illegible]

## 10.5 Study Schedule

### 10.5.1 Screening

The Screening visit will occur within 28 days before dosing on Cycle 1, Day 1. The assessments to be performed at Screening are detailed in the Schedule of Events in [Table 1](#).

### 10.5.2 Treatment

The Treatment Period comprises 28-day dosing cycles. In the absence of unacceptable OP-1250 treatment-related toxicity or disease progression, subjects may receive OP-1250 treatment for up to 1 year and beyond 1 year with the agreement of the investigator or designee and the sponsor. The assessments to be performed at each visit during the cycles of the Treatment Period are detailed in the Schedule of Events in [Table 1](#), [Table 2](#), [Table 3](#), and [Table 4](#).

### 10.5.3 End of Treatment

The EOT visit should occur within 42 days after administration of the last dose of IP.

For any subject who has been withdrawn from the study (see [Section 8.3.3](#)), the tests and evaluations listed for the EOT visit should be performed, if possible. The assessments to be performed at the EOT visit are detailed in the Schedule of Events in [Table 1](#).

### 10.5.4 Safety Follow-up

Safety follow-up should occur at 30 to 42 days after the EOT visit. All related AEs will be followed to resolution, stabilization, or loss of contact with the subject. All unrelated AEs will be followed until the time of the Safety Follow-up visit, which is between 30 to 42 days after the EOT visit. The assessments to be performed at the Safety Follow-up visit are detailed in the Schedule of Events in [Table 1](#).

### 10.5.5 Schedule of Events

The assessments to be performed at each visit during the cycles of the Treatment Period are detailed in the [Table 1](#) (Schedule of Events for All Subjects), [Table 2](#) (Pharmacokinetic and

	OP-1250-001	Page 85 of 111
---	-------------	----------------

Electrocardiogram Sampling Schedule for All Subjects)

#### 10.5.6 Study Stopping Criteria

The study may be prematurely stopped due to the following reasons:

- The discovery of an unexpected, significant, or unacceptable risk to the subjects enrolled in the study.
- A decision on the part of the sponsor to suspend or discontinue the study.
- Any other reason as determined by the sponsor.

The Safety Committee will include investigators participating in the study, the Medical Monitor, and the sponsor's Medical Director and will meet periodically to review all safety and/or PK information in the expansion phase of the study.

## 11 STATISTICAL METHODS AND DETERMINATION OF SAMPLE SIZE

Data collected in this study will be displayed using summary tables, data listings, and graphs. Categorical data will be summarized using contingency tables (frequencies and percentages). For continuous data summary, statistics of mean, standard deviation, median, minimum, and maximum will be presented. Baseline is defined as the last assessment prior to the first dose of study drug.

### 11.1 Analysis Set

#### 11.1.1 Enrolled Analysis Set

The enrolled analysis set includes all subjects who enrolled into the study after signing an ICF and satisfying inclusion/exclusion criteria.

#### 11.1.2 Safety Population

The safety analysis set (SAF) will include all subjects who received at least 1 full or partial dose of OP-1250.

#### 11.1.3 Dose-Limiting Toxicity Analysis Set

The DLT analysis set (DLTAS) will include all subjects in Part A (Dose Escalation) of the study who either received at least 75% of the OP-1250 planned doses or experienced a DLT during Cycle 1. Subjects who do not receive the minimum dosing requirement for a reason other than DLT will be regarded as non-evaluable and may be replaced.

#### 11.1.4 Full Analysis Set

The Full Analysis Set (FAS) will include all subjects who received at least 1 dose of OP-1250 and have at least 1 valid post-baseline tumor assessment.

#### 11.1.5 Efficacy Analysis Set

The efficacy analysis set (EFS) will include all subjects who received at least 1 cycle of OP-1250 and have at least 1 post-baseline tumor assessment.

#### 11.1.6 Pharmacokinetic Analysis Set

The PK analysis set (PKAS) will include all subjects at who received least 1 dose of OP-1250 and have adequate post-baseline PK samples for PK parameters characterization.

### 11.2 Safety Analysis

Safety and tolerability will be assessed by clinical review of all relevant parameters including AEs, DLTs, laboratory values, electrocardiogram results, vital signs, and ECOG PS.

The safety data from Part A (Dose Escalation) will be summarized by dose cohort. The data from Part B (Dose Expansion) will be summarized overall and by *ESR1* mutation status. AEs will be classified by system organ class and PT using MedDRA with severities classified using the NCI-CTCAE, v 5.0 criteria.

All collected AE data will be listed. Separately, all SAEs will also be listed. All TEAEs regardless of attribution will be summarized by cohort, as follows:

- All DLTs (regardless of grade) – DLTAS.
- All AEs (regardless of grade or attribution).
- All Grade 3/4/5 AEs.
- All drug-related AEs (regardless of grade).
- All AEs leading to study drug or study discontinuation.
- All SAEs, including death.
- All AEs of special interest (regardless of grade).

A separate listing of on-study deaths (other than those related to PD) will be presented.

The changes in hematology, chemistry, and other laboratory values will be summarized descriptively for each scheduled protocol assessment time point. Changes will be calculated relative to the values collected at baseline. The incidence of Grade 3 and 4 hematological toxicities (including neutropenia, thrombocytopenia, and anemia) will be provided. The toxicity grades for laboratory tests will be based on NCI-CTCAE, v 5.0 criteria. The use of blood transfusions (platelets, red blood cells) and/or growth factor support will be reported. Similar analyses will be done for selected chemistry tests (including liver and renal function tests). Subject listings of all laboratory data collected during the study will be presented. Laboratory values outside normal limits will be identified in the subject listings and will include flags for high and low values.

Vital sign results (blood pressure, pulse, respirations, and temperature) will be summarized descriptively for each scheduled protocol time point. Changes will be calculated relative to the assessments at baseline.

Extent of exposure for study treatment including number of doses, total dose, dose duration, frequency of dose holding, dose reductions, and dose discontinuations, as well as treatment compliance (percent of actual to planned dosing) will be summarized by cohort.

#### 11.2.1 Electrocardiogram Analyses

The analysis of ECG results will be based on subjects in the SAF with baseline and on treatment ECG data.

ECG measurements (an average of the triplicate measurements) will be used for the statistical analysis and all data presentations. Any data obtained from ECGs repeated for safety reasons after the nominal time-points will not be averaged along with the preceding triplicates. Interval measurements from repeated ECGs will be included in the outlier analysis (categorical analysis) as individual values obtained at unscheduled time points.

QT intervals will be corrected for heart rate, QTc, using standard correction factors (ie, Fridericia's [default correction], Bazett's, and possibly a study specific factor, as appropriate). QTcF will be calculated using the Fridericia formula, as follows:

$$QT_{cF} = \frac{QT}{\sqrt[3]{RR}}$$

Data will be summarized and listed for QT, heart rate, RR interval (RR), PR, QRS, QTc and by study arm and dose. Individual QT (all evaluated corrections) intervals will be listed by study arm time and dose. The most appropriate correction factor will be selected and used for the following analyses of central tendency and outliers and used for the study conclusions. Descriptive statistics (n, mean, median, standard deviation, minimum, and maximum) will be used to summarize the absolute corrected QT interval, and changes from baseline in corrected QT after treatment by study arm dose and time point. For each subject and by treatment, the maximum change from baseline will be calculated as well as the maximum post-baseline interval across time points. Categorical analysis will be conducted for the maximum change from baseline in corrected QT and the maximum post-baseline QT interval.

Changes from baseline for the ECG parameters QT interval, heart rate, RR, QTc, PR interval, and QRS interval will be summarized by treatment and visit (time).

The number (percent of subjects with maximum post-dose QTc values and maximum increases from baseline in the following categories will be tabulated by treatment:

**Table 12: Safety QTc**

	Borderline (msec)	Prolonged (msec)
Absolute Value	$\geq 450 - < 480$	$\geq 480$
Absolute Change	$30 - < 60$	$\geq 60$

If more than 1 ECG is collected at a nominal time post-dose (for example, triplicate ECGs), the mean of the replicate measurements will be used to represent a single observation at that time point. If any of the 3 individual ECG tracings has a QTc value  $\geq 500$  msec, but the mean of the triplicates is not  $\geq 500$  msec, the data from the subject's individual tracing will be described in a safety section of the study report in order to place the  $\geq 500$  msec value in appropriate clinical context. However, values from individual tracings within triplicate measurements that are  $\geq 500$  msec will not be included in the categorical analysis unless the average from the triplicate measurements is also  $\geq 500$  msec. Changes from baseline will be defined as the change between QTc post-dose from the time-matched average baseline triplicates on Day 0, or the average of the pre-dose triplicate values on Day 1.

In addition, an attempt will be made to explore and characterize the relationship between plasma concentration and QT interval length using a PK/PD modeling approach. If a PK/PD relationship is found, the impact of subject factors (covariates) on the relationship will be examined.

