  - iii. Male partner sterilization (at least 6 months prior to screening). For female subjects on the study, the vasectomized male partner should be the sole partner for that subject and the success of the vasectomy must be medically confirmed as per local practice.
  - iv. Placement of a nonhormonal intrauterine device (IUD).
  - b. Additionally, females of childbearing potential, must meet all the following criteria:
    - i. Not pregnant, as confirmed by a negative serum pregnancy test ( $\beta$ -human chorionic gonadotropin) before starting study treatment.
    - ii. Not breastfeeding.
  - c. A female subject is considered to be of childbearing potential unless she meets one of the following criteria:
    - i. Is aged  $\geq 60$  years.
    - ii. Has had a hysterectomy, bilateral tubal ligation, or bilateral oophorectomy.
    - iii. Has medically documented ovarian failure (with serum estradiol and follicle-stimulating hormone levels).
    - iv. Is menopausal (amenorrhea  $\geq 12$  months) while off drugs that interfere with ovarian function.
11. Male subject must be willing to adhere to highly-effective contraception during the study and for 90 days following the last study drug administration. Highly-effective contraception methods must include one of the following criteria:
- a. Successful vasectomy.
  - b. For subjects who have not had a successful vasectomy, and are partners of women of childbearing potential, their partners adhere to any one of the following.
    - i. Hormonal contraception + male subject's use of a condom with spermicide.

- ii. IUD (hormonal or non-hormonal).
  - iii. Bilateral tubal ligation + male subject's use of a condom with spermicide.
  - iv. Depo Provera + male subject's use of a condom with spermicide.
12. Pre and peri-menopausal female subjects must be willing to take a LHRH agonist  $\geq 2$  weeks before the first study drug administration and for the duration of the study.
  13. Subjects must have not taken proton pump inhibitors (PPI) for 7 days prior to first study drug administration and agree to avoid taking PPI therapy for at least the first 2 cycles of therapy.
  14. Subjects must have a corrected QT interval (QTcF)  $< 470$  msec for females and  $< 450$  msec for males (as calculated by the Fridericia correction formula).

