#### **10.2.5 Electrocardiogram**

Triplicate ECGs should be performed after the subject has rested quietly for at least 10 minutes in a supine position. ECGs will be performed in triplicate with a 10-second rhythm strip. When time-matched with a PK sample collection, the ECG should be obtained first. ECGs should be obtained before the assessment of blood pressure and other vital signs.

In some cases, it may be appropriate to repeat abnormal ECGs to rule out improper lead placement as contributing to the ECG abnormality. It is important that leads are placed in the same positions each time in order to achieve precise ECG recordings. If a machine read corrected QT value is prolonged, repeat measurements may not be necessary if a qualified physician's interpretation determines that the QTc values are in the acceptable range. It is preferable that the ECG machine provided for the study is used as it has capacity to calculate the standard intervals automatically.

At each time point, subjects will have 3 consecutive 12-lead ECGs performed 2 to 5 minutes apart to determine mean QTc. If the mean QTcF is prolonged ( $>500$  msec, ie, NCI-CTCAE Grade  $\geq 3$ ), then the ECGs should be re-evaluated by a qualified person at the site for confirmation as soon as the finding is made, including verification that the machine reading is accurate. If manual reading verifies a QTcF of  $>500$  msec, immediate correction for reversible causes (including electrolyte abnormalities, hypoxia and concomitant medications for drugs with the potential to prolong the QTcF interval) should be performed and the Medical Monitor notified.

In addition, repeat ECGs should be performed hourly for at least 3 hours until the QTcF interval falls below 501 msec. If QTcF interval reverts to less than 501 msec, and in the judgment of the investigator or designee and sponsor is determined to be due to cause(s) other than IP, treatment may be continued with regular ECG monitoring. If, in that timeframe, the QTcF rises above 500 msec the IP will be held until the QTcF decreases to 500 msec. Subjects will then restart the IP at the next lowest dose level. If the QTcF has still not

decreased to 500 msec after 2 weeks, or if at any time a subject has a QTcF >515 msec or becomes symptomatic, the subject will be removed from the study. Additional triplicate ECGs may be performed as clinically indicated.

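### Table 12 gives no separate count at 500 msec, and its absolute-value row labels women who enter at 450-469 msec and do not change as post-dose Borderline

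*Protocol*

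**What the plan says.** Protocol Section 11.2.1 plans a categorical analysis by treatment: "The number (percent of subjects with maximum post-dose QTc values and maximum increases from baseline in the following categories will be tabulated by treatment". The categories are in Table 12:

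| Row | Borderline (msec) | Prolonged (msec) |
|---|---|---|
| Absolute value | 450 to <480 | >=480 |
| Change from baseline | 30 to <60 | >=60 |

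The text below the table deals with 500 msec. If one tracing of a triplicate is >=500 msec but the mean is not, "the data from the subject's individual tracing will be described in a safety section of the study report". Such tracings "will not be included in the categorical analysis unless the average from the triplicate measurements is also" >=500 msec. Repeat ECGs taken for safety are handled separately: "Interval measurements from repeated ECGs will be included in the outlier analysis (categorical analysis) as individual values obtained at unscheduled time points". The baseline for the change row is also defined there: "Changes from baseline will be defined as the change between QTc post-dose from the time-matched average baseline triplicates on Day 0", or the mean of the Day 1 pre-dose triplicate.

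Section 10.2.5 ties its response to values above 500 msec, which it equates with CTCAE Grade 3 or higher. The step that triggers correction of causes and notification begins "If manual reading verifies a QTcF of $>500$ msec".

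Inclusion criterion 14 begins "Subjects must have a corrected QT interval (QTcF" and sets the limit at <470 msec for women and <450 msec for men.

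SAP 13.6 plans descriptive statistics for QTcF and heart rate (baseline, maximum post-baseline, change from baseline). It refers to guideline methodology for QT evaluation but lists no categories.

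**The concern.** There are two gaps.

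First, a rule for when a 500 msec value enters the categorical analysis matters only if that analysis has a 500 msec cell. Table 12 has none, so it cannot show how many subjects at each dose reached the level at which the protocol itself acts.

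Second, the absolute row classifies the maximum post-dose value without reference to where the subject started. Its lower cut-point of 450 msec lies inside the range in which women are eligible, so part of the Borderline count describes who was enrolled rather than what happened on drug.

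The study is first-in-human and has no control arm, and Protocol Table 11 gives the QT characteristic of OP-1250 as unknown. No comparator count can be subtracted, so the table has to separate baseline status from on-treatment change itself.

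**Working it through.** The plan states no figure for this point, so there is none to reproduce. The check applies the Table 12 cut-points to example values and then sizes the baseline effect under stated assumptions.

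**Step 1. High values (triplicate means).**

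| Baseline | Maximum post-dose | Absolute row | Change row |
|---|---|---|---|
| 469 | 480 | Prolonged | none (+11) |
| 469 | 499 | Prolonged | Borderline (+30) |
| 469 | 500 | Prolonged | Borderline (+31) |
| 469 | 516 | Prolonged | Borderline (+47) |
| 440 | 485 | Prolonged | Borderline (+45) |
| 440 | 520 | Prolonged | Prolonged (+80) |

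Values from 480 upward all fall in one absolute cell. A mean of exactly 500 msec meets the >=500 wording of Section 11.2.1 but not the >500 wording of Section 10.2.5.

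Two triplicates show how the text rule works. The triplicate 505/498/490 has mean 497.7, so it counts as Prolonged and the single tracing is described in the report. The triplicate 500/470/465 has mean 478.3, so it counts as Borderline and is also described.

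**Step 2. No drug effect (post-dose equals baseline).**

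- Women at 450, 460 or 469 msec: Borderline on the absolute row, nothing on the change row.
- Women at 430 or 449 msec: nothing on either row.
- Eligible men (<450 msec): never Borderline with zero change.

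The change row does not correct the absolute count, because the two rows are not cross-classified. With the same baseline used for both, a woman with baseline >=450 and maximum <480 has a change below 480 - 450 = 30 msec, so she can never appear in the change row.

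**Step 3. Size of the baseline effect.** The documents give no QTcF distribution and no number of women entering at 450-469 msec. The following inputs are assumptions:

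- female mean 420 or 430 msec
- between-subject SD 17
- within-subject SD of a triplicate mean 7 or 10
- entry below 470 msec
- no drug effect

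Protocol Table 2 gives 10 scheduled on-treatment ECG time points: C1D1 post-dose, C1D2, C1D8, C1D15, C2D1 pre- and post-dose, and C3, C5, C7 and C9 Day 1. Each simulated woman is classified by the maximum of 10 triplicate means.

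| Mean, within-subject SD | (a) Borderline | (b) Share of (a) with baseline >=450 | a × b | a × (1 - b) |
|---|---|---|---|---|
| 420, 7 | 0.13 | 0.33 | 0.043 | 0.087 |
| 420, 10 | 0.20 | 0.24 | 0.048 | 0.152 |
| 430, 7 | 0.28 | 0.40 | 0.112 | 0.168 |
| 430, 10 | 0.37 | 0.31 | 0.115 | 0.255 |

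The column a × b is the part due to baseline status: about 4% to 11% of women (the last value is 0.113 before rounding of its factors). The last column is women who started below 450 msec and crossed through noise and the taking of a maximum. They make up 60% to 76% of the null Borderline cases.

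**Step 4. Sensitivity to follow-up.** Observing all 10 time points requires treatment to C9D1. With 7 time points the total in (a) is 12% to 33%, and with 4 it is lower still. The product a × b stays at about 4% to 11%, because it depends mainly on the baseline value.

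**The case against.** The strongest reply is that little is lost. Triplicate means at or above 500 msec are counted, inside >=480. Isolated tracings are described in the report, individual corrected QT values are listed, and a QTcF above 500 msec reported as an adverse event would reach the Grade 3 or higher summaries. The second row of Table 12 is change from baseline, so a woman at 460 msec throughout shows no increase there. The protocol also plans concentration-QT modelling and an optional Frequent ECG sub-study. The SAP lists no categories, so the harm arises only if Table 12 is used as written.

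Much of this stands, and it rules out three stronger readings that a reader might infer:

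- That values of 500 msec or more are never counted. They are counted, but not separately from 480-499 msec.
- That Table 12 ignores baseline. Only the absolute row does.
- That 13% to 37% of women are wrongly classed because of their baseline. That range is the whole null Borderline count. The part already at or above 450 msec is about 4% to 11%.

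The reply does not close either gap. Narratives and listings are not a tabulated incidence by dose, and the adverse-event route depends on reporting. The change row cannot remove unchanged women from the Borderline count. SAP 13.6 neither repairs the categories nor states that they are dropped.

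**Conclusion.** The point holds in this form. Table 12 has no separate 500 msec category, although the text beneath it assumes one and Section 10.2.5 acts at that level, and the two sections state the boundary differently. That finding rests on the documents alone.

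It is also certain from the cut-points that the absolute row counts an unchanged woman entering at 450-469 msec as Borderline. How often this happens is not known. The figure of about 4% to 11% of women rests entirely on the assumed QTcF distribution and no drug effect, with all 10 scheduled on-treatment time points observed.

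A reader might infer that conditioning on baseline would make the count a clean measure of drug effect. It would not: under the same assumptions about 9% to 26% of women (last column of the table) would still appear as new-onset Borderline with no drug effect, because the row uses a maximum over repeated noisy readings.

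This is a reporting weakness in an uncontrolled, descriptive safety analysis. It affects what the table can show, not what data are collected.

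**What to change.** In Protocol Table 12 and SAP 13.6:

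1. Split Prolonged into 480 to <500 msec and a 500 msec category. State one boundary convention for the analysis and word the lower band to match, so that a mean of exactly 500 has one place.
2. Cross-tabulate the maximum post-baseline category against the baseline category, by dose, using <450, 450 to <480, 480 to <500 and the 500 msec category.
3. Report new-onset counts, meaning subjects whose maximum category is higher than their baseline category. For example, 460 to 460 is not new, 440 to 460 is new, 469 to 485 is new, and 469 to 505 is new and appears in the 500 msec category.
4. Keep the 30 and 60 msec change categories.
5. Add a footnote that the cross-tabulation removes baseline status only, and that maxima over repeated readings are biased upward. The footnote should also say how individual repeat ECG values count, since Section 11.2.1 admits them to the categorical analysis.

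Separately, the >500 wording of Section 10.2.5 and the >=500 wording of Section 11.2.1 must be reconciled. Which boundary should govern clinical action is for the sponsor to settle and is not proposed here.

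The cost is a revised table shell and a few lines of SAP text. The ECG data are already collected, and SAP 13.4 already plans shift tables from baseline to maximum post-baseline grade for laboratory values, so the format is in use.
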